5.1.2.2 Day 0, post-surgery, 0 hours (30 minutes post CPB decannulation)

The following evaluations will be performed 30 minutes post decannulation:

- Blood draw for:
 - plasma L-citrulline (*prior to bolus*); 1.0 mL
- Bolus of L-citrulline at 20 mg/kg or placebo 30 minutes after decannulation from CPB immediately followed by a continuous infusion of L-citrulline at 9 mg/kg/hr or placebo for up to 48 hours. The study drug or placebo infusion will be discontinued once invasive arterial blood pressure monitoring is discontinued or at 48 hours, whichever comes first.
- Hemodynamic monitoring including:
 - Heart rate
 - Systemic BP
 - O₂ saturation
 - CVP measurements
 - PAP measurements (if PA line is placed)

Results will be recorded according to the Institution's standard of care from time of post-op admission to the PICU through 48 hours. Results at 1, 2, 4, 12, 24, and 48 hours *from baseline (in OR)* must be obtained and recorded.

ABGs

PaO₂, PaCO₂, HCO₃, and pH measurements
 ABGs will be drawn according to the Institution's standard of care. All results

obtained from the time of post-op admission to the PICU until removal of the arterial line or through 48 hours (whichever occurs first) will be recorded.

- Thoracotomy output measurements (for the duration of chest tube placement)
- Blood draw for:
 - plasma L-citrulline (5 minutes after bolus); 1.0 mL
- Inotrope and other concomitant medication documentation
- Documentation of ventilator settings. Recorded approximately every hour (+/- 10 minutes) from time of separation from CPB until end of mechanical ventilation or 28 days (whichever occurs first)
- Hypotension assessment (Refractory hypotension is defined as a 20% drop of mean arterial blood pressure [MAP] below specific age-related criteria (Haque and Zaritsky (2007) for greater than 30 minutes) (See below)

– Infants: MAP of 40 Age 1 year: MAP of 40 Age 2 years: MAP of 44 Age 3 years: MAP of 47 Age 4 years: MAP of 50 Age 5 years: MAP of 52 Age 6 years: MAP of 53 Age 7 years: MAP of 52 Age 8 years: MAP of 54 Age 9 years: MAP of 55 Age 10 years: MAP of 56 Age 11 years: MAP of 57 Age 12 years: MAP of 58 Age 13 years: MAP of 59 Age 14 years: MAP of 61 Age 15 years: MAP of 62 Age 16 years: MAP of 63 Age 17-18 years: MAP of 64

Adverse events documentation

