7.1.5 Safety Variables

Safety endpoints will be analyzed using the SAF.

Adverse Events

Pre-treatment adverse events and treatment adverse events will be analyzed separately. AEs will be summarized by system organ class (SOC) and preferred term (PT) according to Medical Dictionary for Regulatory Activities (MedDRA). The number of events, as well as the number and rate of affected subjects will be reported. AEs (SOC and PT) will also be summarized by seriousness, as well as by severity and relationship to study medication. No statistical testing procedures will be applied to the analysis of AEs. No statistical testing procedures will be applied to the analysis of AEs.

Incidence of Refractory Hypotension

Refractory hypotension is defined as a 20% drop in mean MAP below specific age-related criteria for more than 30 minutes. The number of subjects with any refractory hypotension from end of surgery until 48 hours will be compared between groups using Fishers' exact test. Additionally, a logistic regression analysis will be applied including factor treatment and site.

Laboratory Values (CBC with differential, serum creatinine and electrolytes & liver enzymes)

The absolute values, absolute and percentage changes from baseline will be tabulated using summary tables listing descriptive measurements for all observed time points. No statistical testing procedures will be applied to the analysis of laboratory values.

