4.9 Data Base Closure and Data Review	20
4.10 Miscellaneous	21
5 CHANGES FROM PROTOCOL	21
6 LITERATURE.....	23
7 APPENDICES	23
8 SIGNATURES	24

List of Abbreviations

In the following abbreviations are listed as used within this statistical analysis plan or which might occur within the tables, listings and graphs outputs:

ABG	Arterial blood gases
ACT	Activated clotting time
AE	Adverse event
ANOVA	Analysis of variance
ASD	Atrial septal defect
ATC	Anatomical therapeutic chemical classification
AVSD	Atrioventricular septal defect
BDR	Blind data review meeting
BMI	Body mass index
BPAP	Bilevel (biphasic) positive airway pressure
CBC	Complete blood count
CI	Confidence interval
CPAP	Continuous positive airway pressure
CPB	Cardiopulmonary bypass
CRF	Case report form
CS	Clinically significant
EC	Exclusion criteria
ECG	Echocardiogram
ET	Early termination
FAS	Full analysis set
FDA	Food and Drug Administration
H0	Null hypothesis
H1	Alternative hypothesis
IC	Inclusion criteria
ICF	Informed consent form
ITT	Intention-to-treat
LOCF	Last observation carried forward
MedDRA	Medical dictionary for regulatory activities
mFAS	Modified full analysis set
N	Number of subjects
NCS	Not clinically significant
OR	Odds ratio
PICU	Pediatric intensive care unit
PP	Per-protocol analysis set
PT	Preferred term
PTAE	Pre-treatment adverse event
RD	Risk difference
RR	Risk ratio
SAE	Serious adverse event
SAF	Safety analysis set
SAP	Statistical analysis plan
SD	Standard deviation
SOC	System organ class
TAE	Treatment adverse event
TLG	Tables, listings, graphs
VSD	Ventricular septal defect
WHO-DD	World Health Organization drug dictionary

No abbreviations of units and of laboratory and blood gas values are included in this list.

1 General

This Statistical Analysis Plan (SAP) was defined by the Sponsor and the responsible Statistician without knowledge of the randomization code. It is based upon the global Study Protocol (version 4.3.1 of August 11, 2017) and the EU Study Protocol (version 2.0 of July 12, 2018) and contains detailed description of the statistical methods described therein.

The SAP describes prospectively the analyses to be performed on study data. It was finalized prior to data base lock and subsequent unblinding.

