4.5 Safety Analysis

Safety endpoints will be analyzed using the SAF.

Adverse events

Pre-treatment adverse events (PTAE) and treatment adverse events (TAE) will be analyzed separately. TAE are defined as all adverse events (AE) with time of onset or worsening on or after the time of first drug administration. If unclear due to incomplete start time / date of AE or drug administration, AEs will be assumed as TAEs.

Adverse events (AE) will be summarized by system organ class (SOC) and preferred term (PT) according to Medical Dictionary for Regulatory Activities (MedDRA) version 19.0. The number of events, as well as the number and rate of affected subjects will be reported for each treatment group. AEs will be summarized also by severity, and by relationship to study medication.

Separate analyses will be done for serious AEs and AEs leading to death.

Preferred terms of AEs with a proportion of $\geq 5\%$ in either L-citrulline or placebo group will be additionally tabulated in descending order of frequency together with the relative risk (RR), risk difference (RD), and Odds ratio (OR).

SAEs will additionally be tabulated by time of onset after time from the end of the surgery (variables "Date of surgery" and "End time" from section/CRF "Surgery"). The following timeframes will be used:

- ≤ 0 hours: Occurrence from time of first drug administration until and inclusive time of end of the surgery
- >0 to ≤ 12 hours: Occurrence after time of end of the surgery until and inclusive + 12 hours
- >12 to ≤ 24 hours: Occurrence after time of end of the surgery + 12 hours until and inclusive + 24 hours
- >24 to ≤ 36 hours: Occurrence after time of end of the surgery + 24 hours until and inclusive + 36 hours
- >36 to 48 hours: Occurrence after time of end of the surgery + 36 hours until and inclusive + 48 hours
- >48 hours: Occurrence after time of end of the surgery + 48 hours until

If unclear due to incomplete start time / date of AE or drug administration, AEs will be assigned to category >0 to ≤ 12 hours.

No statistical testing procedures will be applied to the analysis of AEs.

Incidence of refractory hypotension

Refractory hypotension is defined as dropping of mean arterial (blood) pressure below specific age-related criteria (see below) for more than 30 minutes. I.e., 2 or more successive mean arterial blood pressure (MAP) measurements within a time frame of at least 30 minutes have to be below the criteria as listed below.

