The number of subjects with any refractory hypotension from end of surgery until 48 hours will be compared between groups using Fishers' exact test. Additionally, a logistic regression analysis will be applied including factors treatment and site.

Hypotension assessment (Refractory hypotension is defined as a 20% drop of MAP below specific age-related criteria (Haque and Zaritsky (2007) for greater than 30 minutes):

- Infants: MAP of 40
- Age 1 year: MAP of 40
- Age 2 years: MAP of 44
- Age 3 years: MAP of 47
- Age 4 years: MAP of 52
- Age 6 years: MAP of 53
- Age 7 years: MAP of 52
- Age 8 years: MAP of 54
- Age 9 years: MAP of 55
- Age 10 years: MAP of 56
- Age 11 years: MAP of 57
- Age 12 years: MAP of 58
- Age 13 years: MAP of 59
- Age 14 years: MAP of 61
- Age 15 years: MAP of 62
- Age 16 years: MAP of 63
- Age 17-18 years: MAP of 64

Laboratory values

Laboratory values will be analyzed descriptively. For quantitative parameters, absolute values as well as absolute and percentage changes from Baseline will be tabulated using summary statistics for all observed time points. For qualitative variables, frequency tables will be generated for all observed time points.

A conversion to the given standard units will be performed if necessary. Concentrations below the limit of quantification will be set to zero.

All laboratory values will be classified as normal or abnormal according to the laboratories normal ranges. Abnormal values will be indicated as clinically significant or not clinically significant by the investigator. Shift tables (normal / abnormal, not clinically significant / abnormal, clinically significant) will be created illustrating changes with respect to the laboratories normal ranges and clinical significance between Baseline and post Baseline visits Day 1, Day 2, and Day 28/ Discharge.

The following laboratory parameters were determined and will be described for the corresponding visits:

Hematology

Type of all parameters is quantitative.

- Hemoglobin
- Hematocrit
- Red blood cell (RBC) count
- White blood cell (WBC) count (total and differential)
- Platelet count

Serum Electrolytes, BUN, and creatinine

Type of all parameters is quantitative.

- Serum electrolytes (Na, K, Ca, Mg and Cl)
- BUN
- Creatinine

Liver function tests

Type of all parameters is quantitative.

- Bilirubin (total)
- AP
- AST
- ALT
- LDH

Coagulation

Type of all parameters is quantitative.

- ACT

Urinalysis

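### SAP 4.5 defines refractory hypotension, the only tested safety endpoint, in two conflicting ways, and its age table has no criterion for 5-year-olds

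*SAP*

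**What the plan says.** Protocol sections 5.1.2.2 to 5.1.2.6 and 7.1.5 define the endpoint with a 20% margin. Section 7.1.5 reads: "Refractory hypotension is defined as a 20% drop in mean MAP below specific age-related criteria for more than 30 minutes".

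The SAP, under the refractory hypotension heading of section 4.5, gives two definitions:

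- The first is "Refractory hypotension is defined as dropping of mean arterial (blood) pressure below specific age-related criteria (see below) for more than 30 minutes". The working rule attached to it asks for "2 or more successive mean arterial blood pressure (MAP) measurements within a time frame of at least 30 minutes" under the listed values. It has no 20% factor.
- The second comes after the sentences on Fisher's exact test and logistic regression, and introduces the age table: "Refractory hypotension is defined as a 20% drop of MAP below specific age-related criteria".

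The SAP table has "Age 4 years: MAP of 52" and then goes straight to age 6. Protocol 5.1.2.2 has "Age 4 years: MAP of 50 Age 5 years: MAP of 52". The SAP describes itself as "based upon the global Study Protocol (version 4.3.1 of August 11, 2017) and the EU Study Protocol (version 2.0 of July 12, 2018"). SAP section 5 lists only changes to inotrope time and the inotrope score.

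**The concern.** A binary endpoint needs one rule that sorts each subject into event or non-event. Here the same subsection gives two rules with different thresholds, so the counts in each arm depend on which sentence the programmer follows.

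The endpoint carries weight. It is one of three secondary safety variables. The SAP rules out testing for the other two, adverse events and laboratory values, and 28-day mortality is reported only as a percentage. Refractory hypotension is therefore the only safety outcome with a planned between-group test, although no hypothesis or significance level is stated for it. It also bears on the one potential adverse event the sponsor names: Protocol 1.5 and 6.2.2.1 identify transient systemic hypotension, and Protocol 1.5 reports it in 2 of 11 L-citrulline and 1 of 11 placebo patients in the earlier trial.

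Separately, a 5-year-old has no criterion in the SAP table, and a 4-year-old is judged against a different value from the one in the global protocol.

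**Working it through.** The plan gives no event rate, power or expected count for this endpoint, so there is no figure to reproduce. The check sets the two rules side by side and works out the thresholds.

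**Inputs.** The age criteria come from the tables in SAP 4.5 and Protocol 5.1.2.2. Rule A (first SAP definition) uses the criterion itself. Rule B (second SAP definition, as in the protocol) is read as 80% of the criterion; that reading is an assumption.

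**Formulas.** Threshold A = criterion. Threshold B = 0.80 × criterion. Gap = 0.20 × criterion.

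| Age | Criterion (source) | A | B | Gap |
|---|---|---|---|---|
| Infants, 1 year | 40 (both) | 40 | 32.0 | 8.0 |
| 2 years | 44 (both) | 44 | 35.2 | 8.8 |
| 3 years | 47 (both) | 47 | 37.6 | 9.4 |
| 4 years | 52 (SAP) | 52 | 41.6 | 10.4 |
| 4 years | 50 (protocol) | 50 | 40.0 | 10.0 |
| 5 years | none (SAP) | – | – | – |
| 5 years | 52 (protocol) | 52 | 41.6 | 10.4 |
| 6 years | 53 (both) | 53 | 42.4 | 10.6 |
| 17-18 years | 64 (both) | 64 | 51.2 | 12.8 |

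**Classification.** An infant whose MAP stays above 32 and below 40 for more than 30 minutes is an event under A and not under B. On the 80% reading every B event is also an A event, so in each arm the count under A is at least the count under B. The extra events need not be spread evenly between arms, so the Fisher p-value and the logistic estimate can move either way.

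**Age table.** Settling the 20% question does not settle age 4. Under rule B the SAP value gives 41.6 and the global protocol value gives 40.0, a difference of 1.6. A 5-year-old cannot be classified from the SAP under either rule, yet Protocol 4.3.2 admits subjects up to 18 years. The SAP rows match the table that protocol version 4.3 corrected (Protocol 14.2.4, item 17), although the SAP cites version 4.3.1 as a basis.

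**Duration.** The first SAP definition requires more than 30 minutes, but its working rule requires at least 30. These differ only at exactly 30 minutes. Recording frequency matters more. For post-operative hemodynamics, Protocol 5.1.2.2 says "Results will be recorded according to the Institution's standard of care from time of post-op admission to the PICU through 48 hours". The readings required at every site are at 1, 2, 4, 12, 24 and 48 hours from the operating-room baseline, so the closest pair is 2 − 1 = 1 hour apart. Whether a 30-minute rule can be applied depends on what each site records beyond those times.

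**The case against.** The strongest reply is that the SAP can be read as having one operative rule. Only the first definition comes with a programmable instruction, and the sentence naming Fisher's test follows it directly. The 20% wording sits in the lead-in to the age table, nearly repeats Protocol 5.1.2.2, and may be leftover text. SAP Appendix A was not supplied and might settle the matter. This reading is plausible, but it does not clear the plan. If the first rule governs, the SAP has dropped the protocol's 20% margin without declaring it in section 5. If the second governs, the only working rule in the SAP is wrong.

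Other points on that side:

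- **The rules are nested.** True on the 80% reading, but nested counts are not equal counts.
- **The 20% drop could mean a fall from the subject's own MAP to below the criterion.** That is possible, and the gaps in the table would then not apply. It would still differ from the first definition.
- **The endpoint is secondary, and hypotension is also collectable as an adverse event.** Also true. Preferred terms at 5% or more are tabulated with risk ratio, risk difference and odds ratio. Those are investigator-reported events without a test, and do not replace the MAP-based endpoint.
- **The EU protocol was not available.** The age 4 conflict is therefore shown only against the global protocol. The missing age 5 row and the two definitions are internal to the SAP.
- **The difference between more than and at least 30 minutes is small.** Agreed; it is a wording repair.

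**Conclusion.** The concern holds. SAP 4.5 gives two rules that classify the same child differently, on the only safety endpoint with a planned test, and whichever rule was meant, one part of the plan is wrong as written. Reading the 20% drop as 80% of the criterion, the thresholds differ by 8.0 in infants, rising to 12.8 at ages 17-18. The age table is a lesser but separate defect: no criterion at age 5, and 52 against the global protocol's 50 at age 4.

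The effect on event counts and on the between-arm comparison cannot be quantified from the documents. Which threshold is clinically right is not judged here. The blind data review described in SAP 4.9 covers protocol deviations and assignment to analysis sets, so it is not set up to resolve this. A choice made after unblinding would be open to challenge.

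**What to change.** Before unblinding:

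1. Reconcile the two definitions in SAP 4.5 with each other and with Protocol 5.1.2.2 and 7.1.5. State whether the 20% applies and to what, and whether mean MAP in 7.1.5 means anything different from MAP elsewhere.
2. Use one duration wording, and write the working rule for successive readings to match it.
3. Reconcile the SAP age table with the governing protocol, including the EU version, so that every eligible age has a criterion.
4. Declare any intended departure in SAP section 5.
5. Optionally, report the definition not chosen as a labelled supportive count.

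The cost is SAP wording and programming. First confirm that the MAP readings recorded at every site are frequent enough to apply a 30-minute rule, since post-operative recording follows each institution's standard of care.

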- ⁷ Hemodynamic monitoring includes heart rate, systemic BP, O₂ saturation, CVP, and PAP measurements (if data is available). **Baseline values are first recorded in the operating room (OR)** by Anesthesia. Results will be *monitored* during surgery according to the Institution's standard of care, but results will only be *recorded* approximately every 15 minutes. Standard of care will continue to be followed from time of post-op admission to the PICU through 48 hours. Results at 1, 2, 4, 12, 24, and 48 hours *from baseline (in OR)* must be obtained and recorded.
- ⁸ Arterial Blood Gas (ABG) includes PaO₂, PaCO₂, HCO₃, and pH. ABGs will be drawn according to the Institution's standard of care. Baseline results are first recorded in the OR by Anesthesia. All results obtained during surgery, and from the time of post-op admission to the PICU until removal of the arterial line or through 48 hours (whichever occurs first), will be recorded.
- ⁹ Begin bolus of intravenous (i.v.) L-citrulline at 150 mg/kg or placebo at initiation of CPB & add L-citrulline at a concentration of 200 μmol/L or placebo given as a bolus during bypass. The 200 μmol/L dose may be administered as a one-time bolus or multiple administrations, to maintain the concentration at 200 μmol/L.
- ¹⁰ Collect 1.0 mL of blood for plasma L-citrulline levels (*30 minutes after decannulation from CPB in OR; prior to bolus*). All L-citrulline plasma samples must be processed within four hours of being drawn, stored at -20°F (-28.8°C) or below, and sent on dry ice to the central lab.
- ¹¹ Bolus of 20 mg/kg of L-citrulline or placebo 30 minutes after decannulation from CPB immediately followed by a continuous infusion of L-citrulline at 9 mg/kg/hr or placebo
- ¹² Collect 1.0 mL of blood for plasma L-citrulline levels (5 minutes after bolus). All L-citrulline plasma samples must be

⁵Blood collected for intra-op laboratory values and plasma L-citrulline levels (**10 minutes after study drug administered**); (1.0 mL for plasma L-citrulline). All L-citrulline plasma samples must be processed within four hours of being drawn, stored at -20°F (-28.8°C) or below, and sent on dry ice to the central lab.

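### The refractory-hypotension rule sets no maximum gap between low readings and relies on locally determined charting, so it can join readings many hours apart and can miss real episodes of over 30 minutes

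*SAP*

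**What the plan says.** SAP 4.5 first states the event as a duration: "Refractory hypotension is defined as dropping of mean arterial (blood) pressure below specific age-related criteria (see below) for more than 30 minutes". It then gives the working rule: "2 or more successive mean arterial blood pressure (MAP) measurements within a time frame of at least 30 minutes have to be below" the listed values. That is a minimum span. There is no upper limit on the gap between adjacent readings, no minimum reading frequency and no rule for unobserved time. SAP 4.8 adds that missing safety data are not imputed.

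The analysis is at child level: "The number of subjects with any refractory hypotension from end of surgery until 48 hours will be compared between groups using Fishers' exact test". A logistic regression with treatment and site follows.

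On recording, Protocol 5.1.2.2 (repeated for the 6, 12, 24 and 48 h assessments) says: "Results will be recorded according to the Institution's standard of care from time of post-op admission to the PICU through 48 hours". Footnote 7 of the Schedule of Study Assessments agrees: "Standard of care will continue to be followed from time of post-op admission to the PICU through 48 hours". It makes only these mandatory, counted from the operating-room baseline: "Results at 1, 2, 4, 12, 24, and 48 hours". The denser recording, "approximately every 15 minutes", applies during surgery, before the endpoint window opens.

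The protocol schedule also has a Hypotension Assessment row from 0 to 48 h. Protocol 5.1.2.2 describes it as: "Hypotension assessment (Refractory hypotension is defined as a 20% drop of mean arterial blood pressure [MAP] below specific age-related criteria". No reading interval is given for it.

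**The concern.** A duration is being inferred from intermittent readings whose spacing the plan does not control. Two errors follow. Sparse charting lets two separate low readings stand as one sustained episode. Charting at intervals longer than 30 minutes lets a real episode pass with only one low reading, or none. Whether a child is a case then depends partly on how often that unit writes down a pressure.

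This matters because it is the only safety endpoint with a planned between-group test; SAP 4.5 rules out testing for adverse events and laboratory values. Protocol 1.5 and 6.2.2.1 name transient systemic hypotension as the only potential adverse event of the drug. Misclassification in both directions would weaken the one comparison designed to reveal that harm, and a null result would be hard to read as reassurance.

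**Working it through.** The plan states no expected rate, power or sample size for this endpoint (SAP 1.3 sizes only the primary endpoint), so there is no figure to reproduce. The check applies the rule as written to assumed charting intervals.

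**Missed episodes.** Take an episode of D minutes, readings every d minutes, and a random start. Let s be the smallest multiple of d that is at least 30. The rule is met when readings spanning s fall inside the episode: P = min(1, max(0, (D − s)/d)). So s = 30 for d = 15 or 30, s = 60 for d = 60, and s = 120 for d = 120.

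| Episode (min) | every 15 min | every 30 min | every 60 min | every 120 min |
|---|---|---|---|---|
| 35 | 5/15 = 33% | 5/30 = 17% | 0% | 0% |
| 45 | 100% | 15/30 = 50% | 0% | 0% |
| 60 | 100% | 100% | 0% | 0% |
| 75 | 100% | 100% | 15/60 = 25% | 0% |
| 90 | 100% | 100% | 30/60 = 50% | 0% |
| 120 | 100% | 100% | 100% | 0% |

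All intervals are assumptions. Hourly is not extreme: ventilator settings are recorded about hourly, and Protocol 14.2.4 shows that roughly hourly PICU hemodynamic recording was required until Version 4.3 replaced it with institutional practice.

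**False joining.** The gaps between mandatory readings are 2−1 = 1, 4−2 = 2, 12−4 = 8, 24−12 = 12 and 48−24 = 24 h. Low values at 12 h and 24 h, or at 24 h and 48 h, satisfy the rule if nothing is charted between. As an illustration, suppose only the six mandatory readings existed and each were independently low with probability 0.05 or 0.10. At least one adjacent pair would then be low in 1.2% or 4.6% of children. This leans high, because the earliest readings may precede the end of surgery.

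**Effect on the comparison.** Assume true rates of 2/11 = 18.2% and 1/11 = 9.1%. These are the transient-hypotension counts from the earlier trial (Protocol 1.5), not rates under this definition. Use 95 per arm and two-sided alpha 0.05 (assumed). Observed rate = rate × sensitivity + (1 − rate) × (1 − specificity).

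- Perfect capture: 18.2% vs 9.1%, risk ratio 2.0, Fisher power 37%.
- Sensitivity 0.5, specificity 1: 9.1% vs 4.5%, risk ratio 2.0, power 16%.
- Sensitivity 0.5, specificity 0.95: 0.091 + 0.041 = 13.2% vs 0.045 + 0.045 = 9.1%, risk ratio 1.45, power 10%.

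With assumed true rates of 25% vs 10%, the three powers are 74%, 36% and 22%.

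**The case against.** The strongest reply is that both errors depend on charting frequency, which the documents do not give. In a PICU, eight or more hours without a recorded pressure may be rare, and a charted normal value between two low ones breaks the run because the readings must be successive. This stands. A reader might infer that the rule does misclassify children; the text supports only that it can.

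A reader might also infer bias between arms: faster recovery leads to earlier arterial-line removal, then fewer readings, then fewer detected events. The documents do not support that. Nothing says charting thins after line removal. Treatment is blinded (Protocol 4.4.7), randomization is stratified by site (Protocol 4.2 and 4.4.4), and the logistic model includes site. Sparse charting can also add events by joining distant readings, so the net direction is open.

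A third tempting step is to take the event from the protocol's Hypotension Assessment instead. The documents show a schedule row and a definition, not a separate bedside yes/no record. It may be a review of the same charted pressures. Adopting it would also change the threshold, because the protocol item carries the 20% drop and the SAP working rule does not.

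Finally, hypotension reported as an adverse event is tabulated too, with relative risk, risk difference and odds ratio for terms reaching 5% in either arm. That gives another view of the risk, untested and dependent on investigator reporting. It does not repair this endpoint.

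**Conclusion.** The concern holds as a weakness of a stated rule, not merely as missing detail. The rule has a minimum span and no maximum gap, and the protocol fixes no PICU recording interval, so the rule permits joining readings 12 or 24 h apart. Under hourly charting it cannot detect an episode of 31 to 60 minutes and detects half of those lasting 90 minutes; at 15-minute charting it detects all from 45 minutes. The true size is unknown because actual charting intervals are not in the documents. The detection figures rest on regular charting with random phase, and the power figures on assumed rates, sensitivity and specificity. Some episodes just over 30 minutes escape any discrete charting.

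The likely consequence is an incidence that partly reflects charting density and a diluted Fisher comparison. Directional bias would need charting density to differ by arm, which can be checked but is not shown.

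**What to change.** 1. Reconcile the definition first. SAP 4.5 states the threshold both without and with the 20% drop, and Protocol 5.1.2.2 states it with the drop. SAP 4.5 also uses both more than 30 and at least 30 minutes. The age tables differ: the SAP lists 52 at age 4 and omits age 5, while the protocol lists 50 and 52.
2. In SAP 4.5, require consecutive low MAPs spanning more than 30 minutes, with a pre-specified maximum gap between adjacent readings (for example about 60 minutes plus a charting tolerance). Class sparser stretches as not evaluable for duration.
3. Report MAP readings per child-hour by arm, and state that short episodes cannot be excluded where charting is hourly or sparser.
4. Name the CRF source of the MAP values. If the Hypotension Assessment was captured as a separate record, report it alongside as supportive, not as an automatic replacement.

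The cost is SAP wording and one derivation from data already collected. Some sparsely charted episodes become not evaluable. A strict span over 30 minutes also has a price on an exact 15-minute grid: s rises from 30 to 45, so detection of a 45-minute episode falls from 100% to 0% and is complete only from 60 minutes. The sponsor should choose the span wording knowing this. The cap prevents joining across many hours. It does not recover short episodes under hourly charting, nor separate two dips about an hour apart, which is why the density report and the stated limitation are needed.
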